Post-operative comparison between standard gradient compression dressing vs.
NonCompressive Bioactive Garment on pain, swelling and range of motion following total knee
arthroplasty.

NCT04751942

08-09-2021

PROTOCOL TITLE:

Post-operative comparison between standard gradient compression dressing vs. NonCompressive Bioactive Garment on pain, swelling and range of motion following total knee arthroplasty.

PRINCIPAL INVESTIGATOR:

[name]

[contact]

[contact]

Objectives

This prospective study will evaluate pain, swelling, ROM as well as narcotic use in postoperative total knee arthroplasty patients using novel Non-Compressive Bioactive Garment (NCBG) versus current standard of care gradient compression stocking (Thrombo-EmolicDeterrent or TED hose). If NCBG proves to be more effective in these outcome areas, it will provide a new and comfortable way to reduce patient pain and swelling immediately following surgery.

Background

Total knee arthroplasty (TKA) is one of the most popular surgical procedures today. It is designed and proven to effectively reduce pain caused by end-stage osteoarthritis. Despite its achievements, up to 25% of patients remain dissatisfied after the procedure due to lingering pain, amongst other complaints. Post-operative swelling of the knee and leg is thought to be a contributor to this persistent pain.

Traditionally, a standard gradient compression stocking is applied to the knee and leg after surgery to reduce this pain and swelling. However, due to ineffectiveness or patient noncompliance, compression stockings are often not entirely successful at preventing edema. The recently developed NCPS is a lower extremity garment comprised of a technical fabric that is thought to be able to prevent edema and reduce pain all in a comfortable, user-friendly manner. The purpose of this study is to determine if the NCPS is effective at improving post-operative pain, swelling, ROM and analgesic use associated with TKA.

Pain and prolonged recovery time associated with post-operative swelling are two factors that contribute to patient dissatisfaction following TKA. Swelling of the knee following TKA is caused by intraarticular bleeding and inflammation of the periarticular tissues, which can lead to a decrease in functional performance including pain and delayed rehabilitation. In a study by

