Patients will be approached in the office setting after it has been determined that they have failed conservative management of advanced knee arthritis. Patients will be in the surgeons' clinic behind closed doors with the performing surgeon and another member of the research team. Consent will be obtained in the office after scheduling total knee arthroplasty procedure. The consent process is expected to take 30 minutes, but more time is available to ensure that patients have all their questions answered prior to signing the consent form.

Sharing of Results with Research Participants

- Results will not be shared with research participants
- Results will not be shared with research participants' doctors

Study Design

Prospective randomized control cohort study

Study Procedures

Patients will be enrolled in study prior to surgery, outlined above in the consent process.

At the time of patient enrollment, A trained member of the research team will measure the circumference of the patient's leg at the mid-thigh, mid-knee and mid-calf with the leg in full extension. The patient's range of motion of the operative leg will be measured in flexion and extension. The patient will also fill out a baseline Western Ontario and McMaster Universities Osteoarthritis Index (WOMAC) Questionnaire. All measurements and questionnaire answers will be recorded on the study data collection sheet and will be transferred to RedCAP. At this time, patient's will be assigned a unique study identifier which will be randomly assigned to the experimental or control group. Unique study identifier numbers will start at "#1" and will go up by one additional number with every patient enrolled in the study. Even numbers will be assigned to the control group and odd numbers will be assigned to the study group, ending with 50 people enrolled in each group.

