The patient will then go on to have their primary total knee arthroplasty by standard of care procedure. Both cruciate retaining and posterior stabilized total knee replacement designs will be included in the study. Following closure of the surgical site and placement of a postoperative occlusive dressing, the operative leg will be measured once more for circumference and range of motion, and the values will be recorded on the study data collection sheet and transferred into redcap. The patient will then be placed in their randomized post-operative sleeve/device and will be transferred to the PACU and will receive the standard postoperative treatment.

Pre-operative, intra-operative and post-operative pain protocols will be uniform across performing surgeons and will include pre-operative adductor canal block, intra-operative posterior capsular injection of local anesthetic, and a standardized post-operative medication regimen consisting of:

- Percocet 5/325mg every 6 hours #28 pills
- Ibuprofen 800mg every 8 hours x 14 days
- Carisoprodol 250mg every 8 hours x 14 days
- Gabapentin 300mg every evening x 14 days

- Enteric Coated Aspirin 325mg every 12 hours x 28 days (for DVT prophylaxis)
- Ascorbic Acid 500mg every 12 hours x 14 days
- Colace 100mg every 12 hours for 7 days

On post-operative day one, patient's will be seen and evaluated in their inpatient rooms. Their leg measurements will be taken again with the knee sleeve/compressive gradient dressing pulled down. Measurements will be recorded on the data collection sheet and transferred to RedCAP. Patient's skin will be inspected for any reactions to the sleeve and a standard postoperative examination will be performed to ensure no neurovascular compromise, blood clots, infections or other post-operative complications. The number of oral narcotic pain medications consumed since time of surgery will also be recorded on the data collection sheet and transferred into RedCAP.

Patients will likely be discharged on post-operative day 1. Patients that have not been discharged on post-operative day 1 will not be measured on post-operative day 2.

Sleeves will be worn morning and night for 2 weeks, removing them only for hygiene and washing of the sleeve. After 2 weeks, the patient's will wear the sleeve as much as they can tolerate day and night. At 6 weeks, sleeves will be discontinued all together. Final ROM and Circumference Measurements will be obtained at 12 weeks post-operative mark.

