Visual analog Pain scale
Pain medications consumed
Adverse clinical events including DVT, stroke, PE, surgical site infection, reoperation Name
Medical record number
Patient demographics (age, sex, weight, height, BMI)

Data Analysis Plan

Demographics will be reported using descriptives such as count data and percentages. Differences between groups at baseline (pre-op) will be reported using two-tailed independent ttests for continuous variables, and chi-square or Fisher's Exact tests for categorical data, as appropriate.

The primary outcomes of range of motion, leg circumference, and pain ratings will be compared post-op between conditions using two-tailed independent t-tests. Should clinically relevant

demographics differ significantly between conditions pre-op (baseline), post-op comparisons will instead be conducted using one-way ANCOVAs controlling for differences at pre-op (baseline). These comparisons will additionally be made at multiple additional time-points throughout a 12- week post-op time period.

A priori power analyses were calculated for two-tailed independent t-tests for each primary outcome, using an alpha of .05, power = .80. Each of these are reported and the average of these numbers is used to calculate the final sample size. Clinically significant reductions in pain are defined as a 2-point change with a standard deviation of 2.5 using a 10-point scale; 84 patients were estimated. Clinically significant changes in range of motion are defined as: 10 degrees of difference from a 0-140 degree estimated range of values. Clinically significant changes in leg circumference are defined as: 1 cm difference in leg circumference using a 15-30 estimated range of values. To identify medium effect sizes of .55, 106 patients were estimated. Averaging these values, 99 patients were estimated. To ensure equal numbers of patients in each condition, 100 patients will be recruited for this study.

Risks to Research Participants

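### Site and surgeon are neither on the data list nor in the model, so any variation they cause in ROM and leg circumference stays in the error term of an unadjusted t-test

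*Combined protocol and SAP*

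**What the plan says.** All references are to the combined protocol and SAP.

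- **Sites and surgeons.** Setting names two medical centers and two recruiting office locations. Study Procedures says "pain protocols will be uniform across performing surgeons", so more than one surgeon operates. The number is not given.
- **Implants.** Study Procedures also says "Both cruciate retaining and posterior stabilized total knee replacement designs will be included in the study".
- **Allocation.** The study number "will go up by one additional number with every patient enrolled in the study". Odd numbers go to the garment and even numbers to control, 50 per group. No stratification is mentioned.
- **Analysis.** Under Data Analysis Plan, ROM, leg circumference and pain "will be compared post-op between conditions using two-tailed independent t-tests". ANCOVA takes over only when clinically relevant demographics differ significantly at baseline.
- **Data list.** The demographics named are age, sex, weight, height and BMI. Site, surgeon and implant design do not appear. ROM and circumference are measured at enrolment. The Study Timeline shows no pain rating before post-operative day 1.

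**The concern.** Site and surgeon are structural features of the trial, known before treatment, and could plausibly affect two of the three primary outcomes. Background states that "Swelling of the knee following TKA is caused by intraarticular bleeding and inflammation of the periarticular tissues", which links swelling to the operation itself. Analgesia is standardised across surgeons. The surgery is described only as standard of care.

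The analysis has no place for either factor. The default test ignores them, and the rule that switches to ANCOVA looks only at demographics. Even a gross imbalance between arms in site or surgeon would leave the analysis unchanged. At stake is some avoidable loss of power in a trial that has none to spare for ROM and circumference, and treatment differences that carry chance imbalance which a model could remove.

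**Working it through.** **Inputs from the Data Analysis Plan.** Two-tailed t-test, "using an alpha of .05, power = .80". For ROM and circumference, "To identify medium effect sizes of .55, 106 patients were estimated". The ROM target is "10 degrees of difference from a 0-140 degree estimated range of values". No SD is given, but d = .55 implies 10/0.55 = 18.2 degrees.

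**Assumed, because the documents are silent.** The share of outcome variance explained by site or surgeon (R²), taken as 0 to 10%; the number of surgeons; and equal patient numbers per site or surgeon.

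**1. Reproduce the plan's figure.** Power comes from the noncentral t with noncentrality d·√(n/2) and 2n − 2 degrees of freedom. The smallest n giving 80% at d = .55 is 53 per arm, total 106, as stated. The average (84 + 106 + 106)/3 = 98.7 gives the stated 99, raised to 100.

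**2. Power at the planned size.** With n = 50 per arm, noncentrality = 0.55 × √25 = 2.75 on 98 degrees of freedom, and power is 77.7%. This is already below 80% because 100 is fewer than 106.

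**3. Gain from removing variance.** The effective d is 0.55/√(1 − R²).

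| R² | Effective d | Noncentrality | Power at N = 100 | N for 80% |
|---|---|---|---|---|
| 0 | 0.550 | 2.75 | 77.7% | 106 |
| 2% | 0.556 | 2.78 | 78.5% | 104 |
| 5% | 0.564 | 2.82 | 79.8% | 102 |
| 10% | 0.580 | 2.90 | 81.9% | 96 |

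**4. Cost of the extra terms.** Without stratified allocation, k added terms inflate the variance of the arm effect by about 97/(97 − k) on average and cost k degrees of freedom. Putting this into step 3:

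| R² | Site only (k = 1) | Four surgeons (k = 3) |
|---|---|---|
| 0 | 77.3% | 76.4% |
| 2% | 78.1% | 77.2% |
| 5% | 79.4% | 78.5% |
| 10% | 81.5% | 80.6% |

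Against 77.7%, the net change runs from −0.4 to +3.8 points with site alone and from −1.3 to +2.9 with four surgeons.

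**5. Chance imbalance.** This treats the order in which sites or surgeons enrol as random relative to the odd/even sequence.

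- Two sites (or surgeons) of 50: hypergeometric probability of a 28:22 split or worse is 0.32, of 30:20 or worse 0.07, and of 32:18 or worse about 0.009.
- Four surgeons of 25, as one scenario: at least one is split 16:9 or worse in about 45% of allocations.

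**6. What an imbalance does.** Suppose two equal sites explain 5% of variance. Their means then differ by 2√0.05 = 0.447 SD. A 30:20 split puts 60% of one arm and 40% of the other at the same site, shifting the estimated difference by 0.2 × 0.447 = 0.09 SD, or about 1.6 degrees of ROM at SD 18.2. The target is 10 degrees.

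**The case against.** The strongest reply is that the benefit is speculative. Nothing in the documents says how much variance site or surgeon explains, and below about 2% adjustment gains nothing or costs a little. That stands, and it limits this to a cheap improvement.

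Several stronger readings are tempting, and the documents do not support them.

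- *The t-test is biased or its type I error is inflated.* No. Chance imbalance is not bias, and variation between surgeons is already in the t-test's standard error.
- *Each site's own staff take the measurements, so measurer and site coincide.* Study Procedures says only that a trained member of the research team measures. It does not say whether the sites share measurers.
- *A badly split surgeon is likely.* The 45% depends on an assumed four surgeons. With two surgeons of 50, the proportionally equal split (32:18 or worse) occurs in about 1% of allocations. Alternation also balances more closely if surgeons enrol in consecutive runs.
- *The information is lost.* The medical record number and electronic records are available, so site and surgeon could probably be retrieved. What is missing is a plan to record and use them.
- *Implant design must be adjusted for too.* The arm is assigned at enrolment and the implant is placed later. The documents do not say when the design is chosen or whether the surgeon then knows the arm. It could be a post-allocation variable, and it could largely coincide with surgeon.

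**Conclusion.** The point holds as one of precision and chance imbalance. Site and surgeon are absent from the data list and from the model, and the conditional ANCOVA cannot bring them in. At N = 100 and d = .55, adjustment moves power from 77.7% to somewhere between about 1 point lower (factors irrelevant) and about 3 to 4 points higher (10% of variance explained). At around 5% the gain net of cost is about 1 to 2 points. These figures rest on assumed variance shares and surgeon numbers, and no invalid inference is shown. The change is worth making because the possible loss is small and bounded, and because a model fixed in advance removes a data-dependent choice of whether to adjust.

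**What to change.** 1. Add site and operating surgeon to the data collection sheet.
2. In the Data Analysis Plan, replace the t-test and its conditional ANCOVA with one prespecified linear model for each primary outcome, used whatever the baseline tests show. It should contain arm, site (or surgeon, if there are few surgeons with adequate numbers) and the pre-operative value of the outcome where one is collected. ROM and circumference have one; the pain rating does not. The gain from the baseline value is not quantified here, because the documents give no correlation.
3. Prepare the allocation list separately per site. This also reduces the cost in step 4 of the working. Whether odd/even numbering is predictable is a separate matter.
4. Include implant design only if the planned design is recorded before allocation. Otherwise report it descriptively or in a sensitivity analysis.

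The cost is two fields available from routine records, a rewritten analysis paragraph, one more allocation list, and about 1 point of power or less if the factors explain nothing. No extra patients or visits are needed. Items 1 and 2 can be done at any time before the data are analysed.

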Patients will be asked to fill out the WOMAC questionnaire at the time of consent, postoperative day 1 and at each subsequent post-operative visit.

Patients will be seen back at regularly scheduled post-operative visits of 2 weeks, 4 weeks, 6 weeks and 12 weeks. Patients will be given a WOMAC questionnaire to fill out at each visit. They will also give a numerical score for their perceived average pain level since their last visit. Patients will also be asked to bring in their narcotic pain pills to the post-operative appointment so they can be counted. The WOMAC questionnaire, leg circumference, knee range of motion, average pain score and number of remaining narcotic pain pills will be collected on the data collection sheet and transferred to RedCAP. Any complications will also be recorded.

The Reparel leg sleeve is the experimental device being investigated in this study. It is intended to improve swelling in the post-operative knee. Further description of the device is provided in the background section of this protocol

EPIC Electronic Medical Records will be used to collect data about patients during their inpatient, post-operative stay. Ambulatory EMR will be used in the outpatient setting to collect data and track post-operative clinic visits.

Study Timeline

	Pre-Screening	Time of Consent	Post-op	Post-op day 1	2 week post-op	4 week post-op	6 week post-op	12 week Post-op
Total Estimated time of visit	30 minutes	35 Minutes	5 minutes	30 minutes	30 minutes	30 minutes	30 minutes	30 minutes
WOMAC Questionnaire		x		x	x	x	x	x
Leg Circumference measurements		x	x	x	x	x	x	x
Knee Range-of-motion		x	x	x	x	x	x	x
Review of pain scale and narcotic use log				x	x	x	x	x

The enrollment period will be 1 year from the time of the first patient enrolled in the study. The enrollment period may be expanded to allow for the investigators to reach their goal of 100 patients. The total amount of time each patient will be involved in the study will be 12 weeks. Patients will only be required to wear the post-operative sleeve/dressing for 6 weeks post-operatively. Patients will continue to report their narcotic consumption and average pain scores for 12 weeks post-operatively.

Data to be Collected for your study (AFTER consent and HIPAA Authorization have been obtained)

Mid-thigh, mid-knee, and mid-calf measurements in extension
Range of motion measurements in knee flexion and knee extension
Western Ontario and McMaster Universities Osteoarthritis Index (WOMAC)

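### Circumference and range of motion are compared by unadjusted post-op t-tests by default, so the pre-op values measured on every patient add no precision to the comparison

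*Combined protocol and SAP*

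**What the plan says.** Under Data Analysis Plan, the three primary outcomes (ROM, leg circumference and pain) "will be compared post-op between conditions using two-tailed independent t-tests". The exception is conditional: should clinically relevant "demographics differ significantly between conditions pre-op (baseline), post-op comparisons will instead be conducted using one-way ANCOVAs controlling for differences at pre-op (baseline"). The same comparisons are repeated at further visits up to 12 weeks.

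The trigger concerns demographics. The data-collection list gives these as "Patient demographics (age, sex, weight, height, BMI"). Circumference and ROM are listed there separately.

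Both measures are nevertheless available before surgery on every patient. Study Procedures has circumference taken at enrolment "at the mid-thigh, mid-knee and mid-calf with the leg in full extension", and the "range of motion of the operative leg will be measured in flexion and extension". The Study Timeline confirms both at the time of consent. For pain, the timeline row "Review of pain scale and narcotic use log" starts on post-operative day 1, so no pre-op pain score is scheduled.

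On sample size, the plan states "To identify medium effect sizes of .55, 106 patients were estimated". Averaging across outcomes gives 99, and 100 are to be recruited, 50 per arm.

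**The concern.** Legs differ in size and arthritic knees differ in motion before any operation. Part of the post-op spread is therefore difference between patients that was already present, and the pre-op measurement can remove it. The default t-test leaves that variation in the error term.

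The conditional rule is a poor substitute, for three reasons:

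- It fires on the wrong variables. Read literally, a marked imbalance in pre-op circumference would not start the ANCOVA, while a chance imbalance in age would.
- Baseline p-values choose the model, and 'clinically relevant' is not defined. The primary model is not fixed before the data are seen.
- It does not say whether the covariate is the demographic that differs or the outcome's own pre-op value. Two analysts could fit different models to the same data.

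At stake are the width of the confidence intervals and the power for the two outcomes on which the plan has least to spare.

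**Working it through.** **Inputs from the documents.** Two-sided alpha .05; power target .80; effect size d = .55 for ROM and circumference; 50 per arm; differences of 10 degrees (range 0-140) and 1 cm (range 15-30, no unit given); for pain, 2 points with SD 2.5.

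**Assumed.** The correlation r between the pre-op and post-op value of the same measure, shown over a range.

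**1. The plan's own figure.** For a two-sample t-test with d = .55, noncentral-t power is 79.3% at 52 per arm and 80.1% at 53. So 53 per arm are needed, 106 in total, as the plan states. Also (84 + 106 + 106)/3 = 98.7, the stated 99.

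**2. Power at the planned size, unadjusted.** Noncentrality = d × √(n/2) = .55 × √25 = 2.75 on 98 df, which gives 77.7%. Averaging in the pain figure has taken these two outcomes just below target.

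**3. Power with ANCOVA on the pre-op value.** The residual SD is SD × √(1 − r²), so noncentrality = 2.75/√(1 − r²), on 97 df.

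| r | √(1 − r²) | CI narrower by | Noncentrality | Power | Unadjusted N matching ANCOVA in 100 = 100/(1 − r²) |
|---|---|---|---|---|---|
| 0 | 1 | 0% | 2.75 | 77.7% | 100 |
| .2 | .980 | 2% | 2.81 | 79.4% | 104 |
| .3 | .954 | 5% | 2.88 | 81.4% | 110 |
| .5 | .866 | 13% | 3.18 | 88.2% | 133 |
| .7 | .714 | 29% | 3.85 | 96.8% | 196 |

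The 80% target is restored at r of about .24. A direct simulation of ANCOVA (20,000 trials each) gave 81.2%, 87.8% and 96.8% at r = .3, .5 and .7.

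**4. If the SD is larger than d = .55 implies.** That effect size corresponds to SDs of 1/.55 = 1.82 cm and 10/.55 = 18.2 degrees, which the plan does not state. Taking SD = range/6 instead (an assumption):

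| Outcome | Assumed SD | Unadjusted | r = .3 | r = .5 | r = .7 |
|---|---|---|---|---|---|
| ROM, 10 degrees | 140/6 = 23.3 degrees | 56% | 60% | 69% | 84% |
| Circumference, 1 cm, range read as cm | 15/6 = 2.5 cm | 51% | 55% | 63% | 79% |
| Circumference, 1 cm, range read as inches | 2.5 in = 6.35 cm | 12% | 13% | 15% | 19% |

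**5. What the plan's rule recovers.** The rule was simulated at d = .55 (40,000 trials per setting) with age, sex, height, BMI and weight under assumed adult distributions. Pre-op outcome and BMI were assumed to correlate at .6, and any demographic with p < .05 triggered adjustment. The trigger fired in about 19% of trials.

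| r | Rule, adjusting for the most imbalanced demographic | Rule, adjusting for the outcome's own pre-op value | Unconditional ANCOVA |
|---|---|---|---|
| .3 | 77.5% | 78.6% | 81.2% |
| .5 | 77.8% | 80.1% | 88.2% |
| .7 | 78.1% | 81.7% | 96.7% |

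Under either reading most of the gain is lost. Simulated type I error of the rule, for one outcome at one visit, was 4.4% to 4.9%.

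**6. Pain.** d = 2/2.5 = .80, and power at 50 per arm is 97.7% unadjusted. No power loss is claimed for pain.

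**The case against.** The strongest reply is that the t-test is valid. Under sound randomisation it is unbiased, and the shortfall at the plan's own effect size is only 80 − 77.7 = 2.3 points. That stands: this is a matter of efficiency and clarity, not validity.

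Second, the benefit depends on a correlation the documents do not report. Early ROM could correlate weakly with pre-op ROM, given the nerve block, capsular injection and dressing described in Study Procedures. At r = .1 power is 78.1% and at r = .2 it is 79.4%, a gain below 2 points. That also stands, and the correlation may well differ by visit. It does not favour the t-test, however, since at r = 0 the extra covariate leaves power at 77.7%.

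Third, reading the range 15-30 as centimetres fits poorly with the exclusion of legs over 23 inches (58.4 cm). On an inch reading, adjustment at these correlations would not rescue the 1 cm comparison. This limits the range-based circumference figures but leaves those at d = .55 unchanged.

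Fourth, the trigger could be read generously to include the pre-op outcome values. A rough simulation on that reading gave 22% firing and 80-83% power, so the conclusion hardly moves. The pre-op values may also appear in the baseline between-group tests; they are unused only in the default outcome comparison.

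Finally, the sample-size text speaks of changes, which might suggest change scores. The analysis sentence compares post-op values. In simulation, change scores had less power than ANCOVA in any case (63%, 78% and 94% at r = .3, .5 and .7).

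**Conclusion.** The concern holds. The default analysis of circumference and ROM ignores a covariate already measured on every patient, and the conditional switch seldom uses it. At d = .55 and 50 per arm, unconditional adjustment raises power by 3.7, 10.5 and 19.1 points at r = .3, .5 and .7. Those correlations are assumed, and one value is used for all visits. The defect is lost precision together with a model chosen by baseline significance tests and an unclear covariate. Neither bias nor inflation of per-comparison type I error is claimed, and pain is outside the claim. The change should be made, but the trial's validity does not depend on it.

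**What to change.** In the Data Analysis Plan:

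- Make ANCOVA the primary analysis for circumference and ROM at each visit, whatever the baseline tests show. Regress the post-op value on arm plus the pre-op value of the same measure (same leg level, same direction of motion).
- Name the enrolment measurement as the covariate. Circumference and ROM are also taken after closure, before the sleeve goes on; if that value is to be used, say so in advance.
- Delete the significance-test trigger and report baseline characteristics descriptively.
- Keep the unadjusted t-test as a sensitivity analysis.
- For pain, either keep the t-test or name the baseline WOMAC pain score, collected at consent, as a proxy covariate, and state which in advance.

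The cost is wording only: no new measurement, visit or patient, and one degree of freedom per model.

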Patients will be monitored for allergic reactions and over compression leading to tourniquet effect. There is potential for the experimental garment to not be as effective as the TED hose, which would potentially increase swelling. There is risk of discomfort while wearing the experimental or standard of care garment. Breach of confidentiality is always a concern anytime there is large amounts of patient data being collected, but the risk is being minimized by use of locked storage cabinets for hard copy data and RedCAP for electronic recording of data. There are no perceived psychological, social, legal or economic risks associated with participation in the study. All normal post-operative complications and risks still apply to patients undergoing TKA. Risks associated with the use of the experimental device are expected to be incredibly rare, minor, short lived and completely reversible.

Provisions to Protect the Privacy Interests of Research Participants

Consent will be obtained in a private room at an outpatient clinic facility with solid doors. Consent will be done one-on-one with patients and with another trained members of the research team present in the room.

Potential Benefit to Research Participants

If sleeve is found to be an effective adjunct to decreasing swelling and increase knee ROM, patients will likely have less pain post-operatively and have potential for increased range of motion. If pain is better improved, patients may use less narcotic pain medication which could reduce risk of developing opioid dependence. Patient participation in the study has the potential to benefit society.

Withdrawal of Research Participants

Patients are able to withdraw from the study at any point in time. If this occurs we will use the data we have recorded if possible and the patient will be included in the withdrawn numbers of the study.

Alternatives to Participation

Patients are still free to undergo TKA without needing to participate in the study using the SOC gradient compression dressing

Costs to Research Participants

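### Separate tests at each visit leave missed visits without a method: later comparisons lose precision, and may be biased if loss is outcome-related and differs by arm

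*Combined protocol and SAP*

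**What the plan says.** The Data Analysis Plan states: "The primary outcomes of range of motion, leg circumference, and pain ratings will be compared post-op between conditions using two-tailed independent t-tests". One-way ANCOVA replaces the t-test only if clinically relevant demographics differ at baseline. The plan then says "These comparisons will additionally be made at multiple additional time-points" during the 12 weeks after surgery. The section does not say which visit carries the primary comparison. It names no repeated-measures model, analysis population, missing-data method or expected loss.

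The section Withdrawal of Research Participants lets patients leave at any time and says: "If this occurs we will use the data we have recorded if possible". It also says withdrawals will be counted.

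The Study Timeline schedules circumference and range of motion at consent, immediately after surgery, on day 1 and at weeks 2, 4, 6 and 12. The pain scale starts on day 1. WOMAC is collected at consent, on day 1 and at every later visit.

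**The concern.** An independent t-test at a visit uses only the patients measured at that visit, and so does a one-way ANCOVA. A patient who leaves in week 3 has day 1 and week 2 values, but neither informs the comparisons at weeks 4, 6 and 12. The intention to use recorded data therefore has no analysis behind it for the missed visits.

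Two things are at stake. Precision falls at later visits, in a trial sized with no allowance for loss. Those comparisons are also between the patients who stayed. If patients who are doing badly leave one arm more than the other, that arm looks better than it is. Such a pattern is plausible here: the garments are visibly different and no blinding is described. The risk section mentions discomfort with either garment and the chance that the experimental one controls swelling less well. The Background reports poor compliance with stockings.

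**Working it through.** **Inputs from the plan.** Two-sided t-tests "using an alpha of .05, power = .80"; effect size .55 for range of motion and circumference; pain 2/2.5 = .80; 50 per arm (Study Procedures).

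**Assumptions, because the documents give no figures.** Share missing at a visit 5% to 20%; between-visit correlation .3, .5 and .7, with .6 in step 5.

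**1. The plan's own figure.** Per arm, n = 2(1.960 + 0.842)²/0.55² = 51.9, so 52; the t-based solution is 52.9, so 53, or 106 in total. This agrees with "To identify medium effect sizes of .55, 106 patients were estimated". The average (84 + 106 + 106)/3 = 98.7 gives the plan's 99, rounded up to 100. The component of 84 for pain does not follow from the stated 80% power (26 per arm, 52 in total). That is a separate matter and does not enter the steps below.

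**2. Power of the visit-wise t-test.** With a share m missing, n per arm is 50(1 − m). The t-based power is:

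| Missing | n per arm | Effect .55 | Effect .80 |
|---|---|---|---|
| 0% | 50 | .777 | .977 |
| 5% | 47.5 | .756 | .971 |
| 10% | 45 | .732 | .964 |
| 15% | 42.5 | .707 | .954 |
| 20% | 40 | .681 | .942 |

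**3. What the repeated-measures model recovers without baseline.** With one earlier visit observed and correlation ρ, the effective n per arm is 50/[1 + m/(1 − m) × (1 − ρ²)]. For m = .10 and ρ = .5 this is 50/(1 + 0.1111 × 0.75) = 46.2. Power at .55, by the normal approximation (about one point above the t-based values):

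| Missing | t-test | Model, ρ = .3 | ρ = .5 | ρ = .7 |
|---|---|---|---|---|
| 10% | .742 | .746 | .752 | .763 |
| 20% | .691 | .699 | .713 | .736 |

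The gain is 0.4 to 4.4 percentage points, and no entry reaches .80.

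**4. Bias, by simulation.** 6,000 runs per scenario, normal data, one earlier visit, true difference .55 SD, 10% or 20% missing:

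| Loss pattern | t-test bias (SD) | Model bias (SD) |
|---|---|---|
| Completely random | about 0 | about 0 |
| Driven by earlier value, same in both arms | about 0 | about 0 |
| Driven by earlier value in garment arm only | 0.03–0.15 | about 0 |
| Driven by the unseen value in garment arm only | 0.12–0.23 | 0.06–0.21 |

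In the third pattern the error favours the garment. At the plan's pain SD of 2.5, 0.03 to 0.15 SD is 0.03 × 2.5 = 0.08 to 0.15 × 2.5 = 0.38 points, against a target of 2 points. With no true effect and 10% versus 20% missing, that pattern gave differences of 0.12 SD (ρ = .5) and 0.16 SD (ρ = .7). The t-test's type I error was then 8.5% and 11.1%, and the model's was about 4.9%.

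**5. Where the precision gain comes from.** At correlation .6, simulated standard errors were 0.215 SD for the t-test, 0.209 for the model without baseline, 0.173 for visit-wise ANCOVA on baseline, and 0.171 for the model with baseline. By hand, baseline adjustment alone gives 0.215 × √(1 − 0.6²) = 0.172.

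**The case against.** The strongest case against the point is that several more serious readings fail.

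- A reader might infer that withdrawals bias these comparisons as a matter of course. They do not: step 4 shows about zero bias when loss is random or follows the same pattern in both arms. The documents give no loss rates, and they name discomfort for both garments, so loss driven by outcome in the garment arm alone is an assumption.
- A reader might infer that the undertaking to use recorded data is broken. It is not: a patient who leaves in week 3 still counts on day 1 and at week 2, and the undertaking is qualified. What is missing is a method for the later visits.
- A reader might credit the fall in standard error from about 0.21 to 0.17 SD to the repeated-measures model. Step 5 shows that nearly all of it comes from baseline adjustment.
- A reader might blame loss for the power shortfall. Power at .55 is .777 with nobody missing, because the 106 was averaged down. The power calculated for pain stays above .94 even at 20% loss.
- Stopping the garment is not missing a visit. After week 2 wear is as tolerated, while visits remain scheduled, so discomfort need not cost outcome data.
- The primary visit is unnamed. If it is immediately after surgery or on day 1, few patients would be missing.

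All of this stands, and it limits the size of the concern. It does not supply a method for the missed visits, and the visits that would inform them are already scheduled.

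**Conclusion.** The concern holds in a conditional form. The visit-wise tests discard earlier information on patients who miss a visit. The loss of precision is certain whenever visits are missed: at effect size .55, power goes from .777 to .732 at an assumed 10% loss and .707 at 15%. Bias is possible rather than established. It needs loss that is related to outcome and differs by arm, and in the one-arm scenarios it was about 0.03 to 0.15 SD.

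A repeated-measures model removes that bias when missingness depends on recorded values, and only reduces it when missingness depends on unseen ones. Its own gain in power is small and it does not bring power at .55 to 80%; the shortfall is a sample-size matter. The loss rates and correlations are assumptions, and the bias simulations used a single earlier visit. The concern is greatest if the primary visit is week 12 and slight if it is day 1. The change is worth making because it is cheap and gives the stated intention a method.

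**What to change.** For each primary outcome, make the primary analysis one mixed model for repeated measures:

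- **Patients and visits:** all randomised patients in their assigned arm, with every recorded visit from day 1 to week 12.
- **Terms:** arm, visit and arm-by-visit, with unstructured covariance.
- **Baseline:** for circumference and range of motion, add the baseline value and baseline-by-visit. Pain has no baseline score on its own scale, so omit these terms or use baseline WOMAC pain.
- **Primary visit:** name it, report the arm difference there, and treat the other visits as secondary. The measurement immediately after surgery is taken before the garment goes on, so it cannot show a garment effect.
- **Missing data:** report withdrawals by arm and reason. Add a sensitivity analysis for loss that depends on unseen values, and keep the visit-wise t-test beside it.

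The cost is plan wording and modest programming, with no new data collection. The downsides are reliance on missing-at-random and a result less simple to present than a t-test. An allowance for loss in the sample size is a separate decision that the model does not replace: 106 evaluable patients would need 106/0.9 = 117.8, so 118, at 10% loss, or 106/0.8 = 132.5, so 133, at 20%.
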